7.3.2. Missing Time

For outputs require date and time in calculation, if time is missing or incomplete, the following will be applied:

- If hour and minute are both missing, then the 12:00pm (24hr clock) of the day will be imputed.
- If only minute is missing, the 30th minute of the hour will be imputed.

7.4 Visit Windows

The time schedule described in the protocol for each scheduled activity will be followed as closely as possible. The protocol allowable visit windows in Table 3.1 below will be utilized for analysis purposes. All scheduled visits will be windowed according to the table below.

Table 3.1: Primary Visit Windows

Protocol Visit	Target Day	Protocol allowable window (days)
Screening I (Day -14)	-14	-
Screening II (Day -7)	-7	-
Baseline (Day 0)	0	-
Visit 1 (Day 30)	30	+/- 7 (23 – 44)
Visit 2 (6-Months)	182	+/- 30 (152 – 212)
Visit 3 (9-Months)	273	+/- 30 (243 – 303)
Visit 4 (12-Months)	365	+/- 30 (335 – 395)
Visit 5 (18-Months)	575	+/- 30 (545 – 605)
Visit 6 (24-Months)	730	+/- 60 (670 – 790)
Visit 7 (36-Months)	1095	+/- 60 (1035 – 1155)

If a subject has more than one assessment occurring in the same analysis visit window, the data from the visit closest to the scheduled (target) study day will be used for summaries. If two assessments have the same distance from the scheduled study day, the assessment after the scheduled study day will be used.

If two assessments both occur on the protocol-specified day, and both are valid, then the later one will be summarized. All assessments will be provided in the data listings.

The 9-month primary endpoint analysis will be based on the protocol allowable visit windows. Supportive analysis of the primary efficacy endpoint will be performed using a time to event analysis.

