	
Eligible subjects will undergo a two-week Medical Documentation Screening period to confirm resistant hypertension (SBP <math>\geq</math> 155mmHg) while on maximum tolerable doses of <math>\geq</math> three anti-hypertensive medications from at least three classes of drugs, one of which must be a diuretic.
 
There must be documented clinical evidence to support likelihood of angiographic findings <math>> 80\%</math> whether it is Duplex Ultrasound (DUS), Computed Tomography angiogram (CTa), Magnetic Resonance angiogram (MRa) or other medical evidence. After meeting screening and clinical eligibility criteria, subjects will undergo a baseline assessment for angiographic eligibility. After angiographic documentation of a <math>\geq 80\%</math> diameter renal artery stenosis or Fraction Flow Reserve (FFR) <math>< 0.8</math> is confirmed, the subject may be enrolled in the trial by placement of the investigational device.
 
The 9-month visit will include a follow-up DUS of the target renal artery. If the DUS is non-diagnostic due to an imaging quality problem, such as overlying bowel gas or body habitus, a second DUS may be attempted. If the DUS is indicative of <math>\geq 60\%</math> stenosis as determined by the core laboratory, or the second DUS remains non-diagnostic, a contrast angiogram will be used to assess the degree of restenosis of the covered stent(s).
 
Clinical follow-up visits will be required for all enrolled subjects at 30-days, 9-months, 12-months, 24-months, and 36-months. A 6-month and 18-month visit will occur via telephone to collect medication usage and Adverse Events (AEs) only. The 36-month clinic office visit will be required as the final safety visit.

SUBJECT POPULATION	Subjects who are candidates for a renal artery revascularization with $\geq 80\%$ visual stenosis and have resistant hypertension with $\geq 155\text{mmHg}$ while on $\geq 3$ anti-hypertensive medications from at least 3 classes of drugs, one of which must be a diuretic.
NUMBER OF SUBJECTS	Up to 138 subjects will be enrolled in this trial.
ESTIMATED TRIAL DURATION	The trial duration is projected for 60 months.

ESTIMATED SUBJECT DURATION	Each subject is expected to be enrolled and followed for a total of 36 months.

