#### 4.5.5 18-MONTH (+/- 30 DAYS) PHONE CALL

Trial subject follow-up telephone contact evaluation must occur 18 months post-procedure. The assessment will consist of:

- Collection of concomitant medications
- Collection of AEs, if applicable

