Medications will be tabulated using frequencies and percentages. Subjects may have more than 1 medication per ATC text. At each level of subject summarization, a subject will be counted once if he/she reports one or more medications. Percentages will be based on the number of subjects in the ITT analysis population.

In addition, the number and percentage of subjects using antihypertensive concomitant medications will be summarized by pre-defined categories as recorded in the electronic case report form (eCRF) (diuretics, beta blockers/calcium channel blocker and ACE/ARBs) and presented overall and by study visit.

Use of anti-platelets medication from hospital discharge to three months will be described as the percentage of subjects taking anti-platelet medication at the 3-month follow-up visit.

A subject listing will be presented and include at minimum the medication, drug classification, start and stop dates.

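### SAP Table 3.1 centres the 18-month call on day 575 instead of day 547 or 548, so 44–46% of the protocol's window days fall outside the analysis window

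*SAP*

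**What the plan says.** Protocol 4.5.5 is headed "18-MONTH (+/- 30 DAYS) PHONE CALL" and states: "Trial subject follow-up telephone contact evaluation must occur 18 months post-procedure". It gives no day number. The schedules of events in Protocol Appendix 4 and SAP 7.1 repeat 18 months ±30 days. The Protocol Summary describes the contact: "A 6-month and 18-month visit will occur via telephone to collect medication usage and Adverse Events (AEs) only".

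SAP 7.4 converts the visits to study days. Table 3.1 gives the row "Visit 5 (18-Months") target day 575 and range 545–605. The column is labelled as the protocol's own allowance, and the SAP says: "The protocol allowable visit windows in Table 3.1 below will be utilized for analysis purposes". It adds that every scheduled visit is to be windowed by the table.

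Two outputs can draw on this row. SAP 9.1 counts, at each follow-up time point, the visits observed inside the window, those observed regardless of window, and those expected. SAP 9.8 summarises antihypertensive use by drug category "and presented overall and by study visit".

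**The concern.** Table 3.1 claims to restate the protocol's windows, but for one row it does not. Day 575 is nearly 19 months after the procedure. A programmer following the SAP would treat a call made early in the protocol's window as out of window, and would accept a call made after that window had closed.

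The early calls are not picked up by another visit. The 12-month window closes on day 395 and the 24-month window opens on day 670, so a call shortly before day 545 belongs to no analysis visit. The in-window count at 18 months is at stake and, depending on how it is derived, so is the 18-month column of the antihypertensive summary.

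**Working it through.** **Inputs.** Target days and ranges come from SAP Table 3.1. The ±30 days for the 18-month call comes from Protocol 4.5.5.

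**Step 1: the plan's own figure.** 575 − 30 = 545 and 575 + 30 = 605. The printed range follows from the printed target, so the row is internally consistent. A misread digit is therefore unlikely; the discrepancy lies in the target and carries into the window.

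**Step 2: the table's convention.** Target = months × 365/12.

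| Visit | Months × 365/12 | Table 3.1 | Difference (days) |
|---|---|---|---|
| 6 months | 182.5 | 182 | −0.5 |
| 9 months | 273.75 | 273 | −0.75 |
| 12 months | 365 | 365 | 0 |
| 18 months | 547.5 | 575 | +27.5 |
| 24 months | 730 | 730 | 0 |
| 36 months | 1095 | 1095 | 0 |

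Five of the six rows reproduce within a day. The 18-month row does not: 575 ÷ (365/12) = 18.9 months.

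**Step 3: other conventions.** At 30.4375 days per month, 18 months is day 547.9. At 91 days per quarter it is 546, and at 30 days per month 540. Adding the table's own 12- and 6-month targets gives 365 + 182 = 547. None comes near 575.

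**Step 4: overlap with the SAP window, 545–605 (61 days inclusive).**

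| Target | Protocol window | Shared days | Allowed by protocol, before SAP window | Accepted by SAP, late under protocol |
|---|---|---|---|---|
| 547 | 517–577 | 545–577 (33) | 517–544: 28 of 61 = 45.9% | 578–605 (28) |
| 548 | 518–578 | 545–578 (34) | 518–544: 27 of 61 = 44.3% | 579–605 (27) |

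The result does not hinge on rounding: a target of 546 loses 29 of 61 days (47.5%) and 549 loses 26 of 61 (42.6%).

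**Step 5: a call made on target.** Day 547 or 548 lies inside the SAP window, by 547 − 545 = 2 or 548 − 545 = 3 days. The calls at risk are those made more than 2 or 3 days early.

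**The case against.** The case on the other side leaves the discrepancy alone and disputes its consequences. Most of it stands.

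- **Calls lost.** A reader might infer that about 44% of compliant calls would drop out. That needs calls spread evenly over the 61 days, and nothing in the documents supports this. SAP 7.4 expects the schedule to be kept as closely as possible, and a call on target stays in. The share lost could be zero if every call falls on or after day 545.
- **Medication summary.** A reader might infer that the 18-month antihypertensive summary must be wrong. SAP 9.8 records medications from consent through three years and lists start and stop dates. The SAP does not say whether use at a visit depends on an in-window call or is derived from those dates. If it is derived from dates, no subject is lost, though the reference day could still be off.
- **Site compliance.** A reader might infer that sites would look non-compliant. SAP 9.1 also reports visits regardless of window, SAP 7.4 puts all assessments in the listings, and SAP 9.2 defines deviations against the protocol, not against Table 3.1.
- **Importance.** The contact is a telephone call. No primary endpoint is assessed at 18 months, and 18 months is not a named time point for major adverse events, SBP or eGFR. Enrollment stopped at 68 subjects, and SAP 6.2 makes all inferential analysis descriptive.
- **Exact day.** The protocol prints no day number. Day 548 is an inference; the table rounds fractions down elsewhere (182.5 to 182, 273.75 to 273), which favours 547.

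None of this explains day 575, and the table still governs the analysis as written.

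**Conclusion.** The 18-month row of Table 3.1 is wrong by 27 or 28 days against the table's other month-based rows, and it misstates the protocol window it is labelled as giving. Of the 61 days the protocol allows, 27 or 28 (44–46%) precede the SAP window, and an equal number of days that are late under the protocol are accepted. These are shares of calendar days; the documents do not support turning them into a share of calls.

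The 18-month count of visits observed inside the window would be misstated to the extent that calls fall on the affected days. The by-visit antihypertensive summary may be affected, depending on a derivation the SAP leaves open. The point is minor and touches no primary endpoint.

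One assumption carries the result: that 18 months is converted to days as in the table's other rows. The choice between 547 and 548 moves the figure by one day in 61.

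**What to change.** Correct the 18-month row of SAP Table 3.1 to target day 547 with range 517–577, or day 548 with range 518–578. Day 547 matches the table's habit of rounding down; either agrees with the protocol's 18 months ±30 days. Make the change before the by-visit tables are programmed.

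The cost is one table row. It alters only how calls are assigned in the analysis. Data collection, the timing of the call and the primary analysis are unchanged.

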7.6 Endpoints, Safety Outcomes and Other Parameters

7.6.1.Primary Endpoints

Primary Patency Rate

In order to mitigate the challenges with DUS interpretation, clinical validation through independent noninvasive core laboratory and/or angiography will be performed in order to correctly validate and definitively assess percent diameter stenosis. DUS is highly reliable in identifying widely patent stents – however, correlation studies of DUS with angiography have confirmed that DUS is not as accurate when results suggest a stenosis. To lessen the risk of inaccurate readings, if a stenosis is detected in DUS (RAS > 60%) or if the DUS is non-diagnostic due to an imaging quality problem then a contrast angiogram will be used to assess the degree of restenosis of the covered stent(s) at the 9-month visit (± 30 days).

The primary efficacy variable is the primary patency rate, defined as continuous patency without the occurrence of a total occlusion (complete obstruction or a closure of a passageway or vessel determined by DUS or contrast angiogram) of the original lesion, and

Amendment #1: 15Jul13

Confidential

- without a re-intervention due to a clinically driven restenosis or occlusion to treat a partial or total occlusion of the stented segment,
- or bypass of the stented segment due to clinically-driven restenosis or occlusion

The primary patency will be calculated on a per lesion basis – for purpose of analysis in cases in which multiple lesions are covered by one stent then the stented segment will be considered as one lesion. The cumulative incidence of patency at 9 months will be computed as the number of lesions that met primary patency divided by the number of subject-lesions for the population being analyzed.

Change from Baseline in Systolic Blood Pressure

Systolic blood pressure will be assessed at each follow-up study visit. Blood pressure measurements will be obtained with a certified, calibrated, and validated equipment. Subjects will be instructed to refrain from exercise, smoking or caffeine ingestion for 30 minutes before blood pressure measurement, and measurements will be obtained after at least 5 minutes of rest. At each time point, a minimum of three (3) readings separated by 2 minutes will be averaged.

The primary clinical outcome is the improvement in systolic blood pressure (SBP) at 9-months as compared to baseline systolic blood pressure computed as follows:

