9.9.1. Primary Patency Analysis

The primary endpoint will be the cumulative incidence of primary patency at 9-months of study computed as the number of subjects with primary patency at 9-months divided by the number of subjects in the ITT population. An exact binomial one-sided 95% confidence interval will be constructed and the upper limit compared to the Performance Goal equal to 70%. A p-value for the one-sided exact test of the difference between the observed rate and the Performance Goal will be presented. The primary analysis will be analyzed with observed data only.

A planned subgroup analysis of the primary functional endpoint will be performed (details are provided in section 9.9.4

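### SAP 7.4 excludes from 9-month patency a confirmatory angiogram or first image obtained after day 303, and leaves unclear which in-window image governs

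*SAP*

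**What the plan says.** SAP 7.4 (Table 3.1) sets the 9-month target at day 273 with an allowable window of days 243 to 303. It states that "The 9-month primary endpoint analysis will be based on the protocol allowable visit windows". If one window holds more than one assessment, "the data from the visit closest to the scheduled (target) study day will be used for summaries", with a tie rule: "If two assessments have the same distance from the scheduled study day, the assessment after the scheduled study day will be used". Imaging type is not mentioned.

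Patency imaging is sequential. Protocol 3.0 describes a DUS, possibly a second DUS, and then a contrast angiogram if the core laboratory reads at least 60% stenosis or the second DUS is still unreadable. SAP 7.6.1 says that "if the DUS is non-diagnostic due to an imaging quality problem then a contrast angiogram will be used", as it is when the DUS detects a stenosis. It places that angiogram at the 9-month visit, within 30 days either side. The same section says that DUS is less accurate when it suggests a stenosis.

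Under SAP 7.6.1 patency is lost through total occlusion (by DUS or angiogram), clinically driven re-intervention, or bypass. On missing results, SAP 9.9.1 says "The primary analysis will be analyzed with observed data only".

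**The concern.** The angiogram follows the DUS, its reading and perhaps a repeat scan, yet it gets no extra time. A DUS late in the window can therefore push the angiogram past day 303. The image meant to settle the question is then unusable. An unreadable DUS leaves the lesion without a 9-month result, and a suspicious DUS stands uncorrected.

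A subject whose first 9-month image comes after day 303 is also lost. Yet if that image shows no occlusion and no failure event came before it, the definition of continuous patency means the stent was patent on day 273.

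The lesions exposed are not a random sample. They are those with a non-diagnostic DUS, those where DUS and angiogram disagree on total occlusion, and those imaged late. What is at stake is the co-primary patency rate compared with the 70% performance goal.

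**Working it through.** **1. The plan's own window.** 273 − 30 = 243 and 273 + 30 = 303, as stated. The 12-month window opens at 365 − 30 = 335. Days 304 to 334, 31 days in all, belong to no window.

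**2. The rule applied literally.** Let the DUS fall on day t (243 to 303, so 61 possible days) and the angiogram on day t + L. The documents give no lag, so L is an assumption, shown over a range.

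- Angiogram out of window: t + L > 303, which covers L of the 61 days.
- Both in window, DUS nearer: |t + L − 273| > |t − 273|, that is t > 273 − L/2, with t ≤ 303 − L.
- Angiogram nearer or tied: the remaining days (a tie goes to the later image).

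| Lag L (days) | Angiogram out of window | DUS nearer (DUS days) | Angiogram nearer or tied |
|---|---|---|---|
| 7 | 7 (11%) | 27 (44%; 270–296) | 27 (44%) |
| 14 | 14 (23%) | 23 (38%; 267–289) | 24 (39%) |
| 21 | 21 (34%) | 20 (33%; 263–282) | 20 (33%) |
| 30 | 30 (49%) | 15 (25%; 259–273) | 16 (26%) |

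The out-of-window column needs only the day-303 limit. The DUS-nearer column matters only if the nearest-day rule is applied across imaging types. The percentages are shares of possible DUS days. They illustrate the rule and do not forecast how many lesions will be affected.

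**3. What happens to a lesion whose angiogram falls after day 303.**

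- DUS non-diagnostic: no observed result, so the lesion drops out, whether patent or occluded.
- DUS suggests occlusion, angiogram shows a patent stent: counted as a failure, so the rate is too low.
- DUS suggests stenosis without occlusion, angiogram shows occlusion: counted as patent, so the rate is too high.
- DUS and angiogram agree on occlusion status: no change.

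For a first image after day 303, a patent stent or an occlusion is discarded alike.

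**4. Weight of one lesion.** SAP 6.1 gives 68 subjects and SAP 5.2 cites 1.2 lesions per subject: 68 × 1.2 = 81.6, about 82 lesions. At the planned 82% patency, 0.82 × 82 is about 67 patent lesions, and 67/82 = 81.7%.

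- One failure counted as patent: 68/82 = 82.9% (+1.2 points).
- One patent lesion counted as a failure: 66/82 = 80.5% (−1.2 points).
- One failure dropped: 67/81 = 82.7% (+1.0 point).
- One patent lesion dropped: 66/81 = 81.5% (−0.2 points).

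**5. Whether another analysis would reveal it.** SAP 8.3 drops imputation. SAP 6.2 and 9.9.3 limit sensitivity analysis to the per-protocol population. SAP 7.4 promises that "Supportive analysis of the primary efficacy endpoint will be performed using a time to event analysis", but SAP 6.2 and the only specification, in 9.11.11, concern revascularization. An occlusion that is not treated is not an event there. SAP 9.1 tabulates visits both within and regardless of window, so out-of-window visits are foreseen, but that table does not classify patency.

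**The case against.** The strongest reply is that SAP 7.4 windows scheduled visits and selects data for summaries. It reads naturally as a rule for repeats of the same assessment. DUS and angiography are separate rows in the schedule and are reported separately (SAP 9.11.8 and 9.11.10). The endpoint-specific text in 7.6.1 sends the reader to the angiogram. All of this stands. A reader might infer that the SAP makes DUS outrank the angiogram. It does not say so. The two sections are silent on which governs, and that silence is the defect.

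A reader might also infer that an in-window angiographic occlusion could be lost behind a nearer DUS. The documents do not support that: total occlusion shown by either method is a failure by definition. Nor is stenosis of 60% or more a failure in itself. A re-intervention on, say, day 320 is reasonably an event after the 9-month window.

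Finally, enrolment stopped at 68, all inference is to be read as descriptive, and SAP 7.2 refers 9-month data handling to a data management plan that is not among the documents. These points limit the consequence but do not remove it. The patency estimate is still reported and still compared with 70%, and the rule that derives the endpoint belongs in the SAP.

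**Conclusion.** The concern holds in a narrow form. Followed as written, SAP 7.4 discards an angiogram after day 303 even when an in-window DUS prompted it, and discards a late first image. If the nearest-day rule is applied across imaging types, it also conflicts with 7.6.1 on which in-window image governs.

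The direction of bias is open and its size cannot be derived from the documents. It is tempting to apply an assumed late share, say 10% to 40%, to the whole planned failure rate of 18% and report an inflation of several points. That is not supported. The 18% includes re-interventions, bypasses and occlusions already seen on an in-window DUS, none of which depends on a late angiogram. What can be said is that one misclassified lesion among about 82 moves the rate by about 1.2 points.

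This rests on three assumptions: that 1.2 lesions per subject applies here; that the observed-data statement in 9.9.1 removes unclassified lesions from the denominator, although the same section also divides by the ITT population; and that an occluded stent does not reopen without treatment.

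**What to change.** In SAP 7.4, exempt patency imaging from the nearest-day rule and add:

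- An angiogram prompted by the 9-month DUS supersedes that DUS and belongs to the 9-month assessment, even if performed after day 303.
- If no image falls in days 243 to 303, the first later image decides. No occlusion and no earlier failure event means patent at 9 months; occlusion means failure.
- Re-interventions and bypasses are classified by their event date.
- The strictly windowed result is reported as a sensitivity analysis.

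The cost is a few lines of SAP text and one derivation rule, with no new data. The downside is that an occlusion arising shortly after day 303 may be charged to the 9-month rate, making it slightly less favourable. The windowed sensitivity analysis would show how much that matters.

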7.5 Baseline Assessments

- Inclusion/exclusion criteria

Amendment #1: 15Jul13

Confidential

- Demographics (age, gender, race/ethnicity)
- Collection of targeted medical history
- Collection of focused anti-hypertensive medical history
- Height/weight
- Vital signs
- Collection of blood pressure
- Laboratory assessments:
 - Chem12 Panel which includes: Glucose, Calcium, Albumin, Total protein, Sodium, Potassium, CO₂, Chloride, BUN, creatinine, ALP, ALT, AST, and bilirubin.
 - Test for proteinuria. Urine proteinuria may be tested by dipstick. A level of > 2+ is exclusionary unless a 24 hour urine shows that the urinary protein is < 2gm/d.
 - Pregnancy Test
- Physical exam
- Collection of concomitant medications
- Collection of Adverse Events (AEs), if applicable

